3.2 Secondary objectives and secondary endpoints

The purpose of the clinical trial is to secondarily investigate whether albumin administration and the maintenance of serum albumin concentrations of at least 30 g/l for 28 days after the onset of septic shock will influence 28- and 60-day mortality, ICU and hospital mortality rates, organ dysfunction/failure as assessed by the SOFA score, ICU and hospital lengths of stay, as well as ventilator- and vasopressor-free days. A cost-benefit analysis of the volume replacement therapy for the ICU stay up to a maximum of day 28 is another objective of this clinical trial.

Secondary end-points therefore are

- 28- and 60-day mortality,
- ICU and hospital mortality,
- organ dysfunction/failure as assessed by the SOFA-Score: recorded daily up to 28 days in the ICU after randomisation in the study,
- ICU and hospital lengths of stay.
- ventilator- and vasopressor-free days,
- cost-benefit of volume replacement therapy: collection of data on the use of human albumin and other colloids and crystalloids,
- · Total amount of fluid administration and total fluid balance, and
- safety-related parameters: occurrence of AEs and SAEs, especially anaphylactic shock, hypervolaemia, and pulmonary oedema.

4. Trial design

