7.5 Trial visits on trial days 1 to 28 after randomisation

These visits should only be performed if the patient is still being treated in the ICU.

- Blood sampling to determine the serum albumin concentration, including recording the time of blood sampling
- Blood samples for serum albumin concentration determination may be performed as part of the routine blood sampling procedure at the respective trial centre, provided that they are taken between 4:00 and 9:00 in the morning.
- Collection of data on infection, microbiology and anti-infective therapy
- Recording of the raw data for calculation of the SOFA score on the respective study day from the routine laboratory results (not for trial purposes); the "worst" daily value should be recorded
- Recording of concomitant medication with catecholamines and inotropes, diuretics, fluid therapy (including transfusion therapy, adjunctive sepsis therapy) on the respective trial day
- Recording of intensive care interventions (ITN, CIC, AC, RRT, mechanical ventilation, ECMO, haemodynamic monitoring) on the respective trial day
- Recording the amount of enteral and parentral fluid adminstration on the trial day
- Collection of routine laboratory data (not trial-related), taken between 4:00 9:00 in the morning: haemoglobin, creatinine, bilirubin, C-reactive protein, procalcitonin, leucocytes, platelets, lactate, arterial blood gas analysis (PaCO2, PaO2, FiO2, SO2, pH, ScO2)
- Recording of clinical parameters (body temperature, respiratory frequency and haemodynamic parameters), 24 h urinary output, other fluid loss on the trial day
- Capturing of AEs/SAEs and sepsis-related clinical events (continuous)
- Recording of vital status (live / dead)
- Albumin group: administration of the trial drug according to serum albumin concentration, dose adjustment according to the given scheme
- Data collection regarding administration of the trial drug (continuous), including information on the administered dose, interruption or discontinuation of the dose if necessary Note: After administration of the trial drug on day 28, no further doses are given.

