7.5.1 Data collection at hospital discharge or at the end of the study

Data will be collected from participants at one of the following time points, whichever comes first:

ZKSJ0112 ARISS

- Discharge from the hospital before or on trial day 28
- Discharge from the hospital up to and including trial day 90
- Trial day 90 reached in the hospital (regular end of study)
- Early termination of the clinical trial as described in 7.6

Data collection:

- Recorde data on ongoing SAEs and serious sepsis-related clinical events
- Vital status (alive/dead): if applicable date of death and cause of death; if applicable, recording of "end of life" decisions, stay after discharge
- ICU length of stay (of the first ICU stay after study participation)
- Hospital length of stay (first hospital stay after study participation)

If the patient is discharged from the ICU or the hospital during the 90-day observation period, this time will be defined as the endpoint for determining the ICU length of stay and/or hospital stay. If the patient returns to the ICU or hospital within the 90 days, this is no longer relevant for the collection of trial endpoints.

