11.3.2 Data analysis

General methodology:

All collected data will be analysed using descriptive methods in the two treatment groups. This includes at least:

- the number of values collected and missing, mean, standard deviation, minimum, quartiles including median and maximum for continuous variables and
- frequency analyses for ordinal and categorical data.
- At baseline, the last available value will be used no later than the period up to 2 hours after randomisation, but before the start of albumin administration.

Baseline and population characteristics, demographics:

Demographic variables, SAPS II, APACHE II: descriptive analysis

Primary analysis:

The primary endpoint, "90-day mortality" (M90), will be calculated using a generalised mixed model with the random effects "centre" and "patient in centre" and the fixed effects SAPS II, SOFA and "baseline serum albumin value" as well as " treatment group "to the significance level Alpha = 0.05 analysed bilaterally.

The null hypothesis, M90 (control group) = M90 (albumin infusion), will be tested against the alternative M90 (control group) \neq M90 (albumin infusion).

The primary analysis will be conducted in the ITT population.

Additional sensitivity analyses:

- Analysis in the PP population
- If more than 10% of M90 data are missing: multiple imputation analysis based on observed mortality rates, SOFA scores, ICU stay, and hospital stay.

Secondary endpoints:

- 28-day, 60-day, intensive care and hospital mortality: descriptive statistics, Kaplan-Meier estimates on mortality.
- Organ failure defined as increase in the daily recorded SOFA (day 1 to 28) from a value <2 to a value ≥ 2, individual number of organ failures in the period from day 1 to day 28: descriptive statistics, Kaplan-Meier estimates for the date of the individual first organ failure
- SOFA score: descriptive statistics
- Length of stay (after randomisation, until first discharge) in ICU, hospitalisation after randomisation (until first discharge to rehabilitation, transitional care, long-term care or home): descriptive statistics, Kaplan-Meier estimates, censored after drop-out and death.
- Ventilation-free days, vasopressor-free days until (first) discharge of ICU or maximum 28 days: descriptive statistics

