Appendix 14.

14.1 SOFA Score

Organ dysfunction is defined according to the SOFA score variables. The worst value of the parameter each day will be used to calculate the score. The parameters of the SOFA score are determined until day 28 exclusively in the intensive care unit and are calculated from the sum of the evaluation points of the individual organ systems listed below. The parameters for calculating the SOFA subscore are also part of the CRF. The score points of each organ system range from 0 to 4. The SOFA score is calculated in the data management center (ZKS Jena). The subscores of the SOFA score are determined as follows:

Cardiovascular System

Mean arterial pressure (MAP) and the need for catecholamine determine the assigned points. The lowest MAP value of the past 24 hours is part of the CRF. The highest catecholamine dosage> 1 h of the past 24 hours is part of the individual variables in the CRF.

Score	Cardiovascular status				
0	MAP ≥ 70 and no vasopressors				
1	MAP < 70 and no vasopressors				
2	Dopamine <5 μg/kg/min oder Dobutamine (and dose)				
3	Dopamine >5 – <15 μg/kg/min or (nor)adrenalin <0.1 μg/kg/min				
4	Dopamine>15 μg/kg/min or (nor)adrenalin >0.1 μg/kg/min				

Pulmonary system

The PaO₂/FiO₂ ratio determines this sub-score. If the blood gas analysis is not available for the day or the patient is no longer intubated, but relies on oxygen therapy, conversion tables will be used.

Score	PaO ₂ /FiO ₂
0	> 400 mmHg (> 53.2 kPa)
1	301–400 mmHg (39.9–53.1 kPa)
2	201–300 mmHg (26.6–39.8 kPa)
3	101–200 mmHg (13.3–26.5 kPa)
4	< 100 mmHg (< 13.3 kPa)

Coagulation system:

The platelet count determines this sub-score. The lowest platelet count of the past 24 hours is part of the CRF variables.

Score	Platelet count
0	$>150 \times 10^{3} / \text{mm}^{3}$
1	100-149 ×10 ³ /mm ³
2	50–99 ×10 ³ /mm ³
3	20–49 ×10 ³ /mm ³
4	$<20 \times 10^{3} / \text{mm}^{3}$

Serum creatinine and urinary output determine this sub-score. The worst value is part of the CRF variables.

Zentrum für Klinische Studien

Score	Serum creatinine and urinary output			
0	<1.2 mg/dl (<110 µmol/l)			
1	1.2–1.9 mg/dl (110 –170 µmol/l)			
2	2.0-3.4 mg/dl (171- 299 µmol/l)			
3	3.5–4.9 mg/dl (300–440 µmol/l) or urinary output <500 ml/24h			
4	≥5,0 mg/dl (≥ 441 µmol/l) or urinary output <200 ml/24h			

Hepatic system:

Total bilirubin determines this value. The worst value is part of the CRF variables.

Score	Total bilirubin
0	<1.2 mg/dl (< 20 µmol/l)

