6.7 Secondary Analyses

28- and 60-day-mortality, mortality rate at ICU and in-hospital mortality will be analyzed descriptively. Overall mortality will be described by Kaplan Meier methods.

SOFA score will be analyzed descriptively over time, for organ subscores frequency analysis will be presented. Number and % of patients with organ dysfunction defined as any subscore > 2 and number of patients with organ failure defined as any subscore >3 will be given. Duration of stay on ICU and duration of hospitalization, days not requiring artificial respiration

and days without vasopressors will be analyzed descriptively.

Amount of albumin applicated, other colloids and crystalloids will be analyzed descriptively over time.

Overall fluid intake and overall fluid balance will be analyzed descriptively over time. Definition [1] for overall fluid output will be used, if 90% of perspiration values are given If perspiration is missing in more than 10% of visits n patients, definition [2] excluding perspiration will be used for main analysis. Analysis in subgroup with perspiration available will be performed as additional sensitivity analysis.

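### The protocol plans Kaplan-Meier for first organ failure, an event seen only in living ICU patients, with no rule for ICU death or discharge; the SAP reports counts under another threshold and does not declare the change

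*Protocol*

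**What the plan says.** - **Event and method.** Protocol 11.3.2 gives "Organ failure defined as increase in the daily recorded SOFA (day 1 to 28) from a value <2 to a value ≥ 2" and, for the first such event, "Kaplan-Meier estimates for the date of the individual first organ failure".
- **Observation window.** Protocol 3.2 lists the SOFA endpoint as "recorded daily up to 28 days in the ICU after randomisation in the study". Appendix 14.1 says it is "determined until day 28 exclusively in the intensive care unit". On the daily visits, Protocol 7.5 says "These visits should only be performed if the patient is still being treated in the ICU".
- **Readmission.** Protocol 7.5.1: "If the patient returns to the ICU or hospital within the 90 days, this is no longer relevant for the collection of trial endpoints".
- **Censoring.** None is stated for organ failure. In the same list in 11.3.2, length of stay is given a rule that treats death and drop-out as censoring.
- **SAP.** Section 6.7 plans the number and percentage of patients with organ dysfunction (any subscore above 2) and "number of patients with organ failure defined as any subscore >3 will be given". It uses Kaplan-Meier for overall mortality only. Section 6.11 declares one change from the protocol, the subgroup cut-points.

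**The concern.** A first organ failure can be observed only in a patient who is alive and still in the ICU. Death makes the event impossible. Live discharge ends observation, and it tends to remove the patients least likely to have the event. Neither is non-informative censoring. If both are censored, one minus Kaplan-Meier (1-KM) estimates a risk in a setting where nobody dies or leaves the ICU, not the proportion of randomised patients who develop new organ failure.

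Competing death is large here. Protocol 8.2 cites 47% ICU mortality in severe sepsis and septic shock, and 11.1 assumes about 50% 90-day mortality in the control arm. Organ dysfunction/failure is a named secondary objective, and 11.3.2 foresees exploratory comparisons of secondary endpoints between the arms. If albumin keeps sicker patients alive, they stay at risk longer, and a display of organ failure alone can look worse in the arm with better survival.

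**Working it through.** Neither document gives an organ-failure rate, an ICU discharge rate or the timing of failures. There is therefore no stated figure to reproduce, and every hazard below is an assumption.

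**1. Formulas.** Let h1 be the daily hazard of first organ failure and h2 the daily hazard of ICU death or live discharge, both constant to day 28, with death and discharge censored in the Kaplan-Meier estimate.

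- 1-KM = 1 − exp(−28·h1)
- Cumulative incidence = h1/(h1+h2) · [1 − exp(−28·(h1+h2))]

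**2. One example.** Take h1 = 0.04 and h2 = 0.03 (death) + 0.05 (discharge) = 0.08.

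- 1-KM = 1 − exp(−1.12) = 67.4%
- Cumulative incidence = 0.04/0.12 · [1 − exp(−3.36)] = 32.2%
- Ratio = 67.4/32.2 = 2.1

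**3. Range.** Set h2 = ln 2 / (median days to ICU death or discharge), solve h1 for an assumed true 28-day risk, and take the ratio of 1-KM to that risk. For a median of 10 days and a true risk of 30%, h2 = 0.0693 and h1 = 0.0324, so 1-KM = 59.6% and the ratio is 1.99.

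| Assumption | True 28-day risk | Ratio of 1-KM to true risk |
|---|---|---|
| Constant hazard, median 5 days | 10–70% | 3.55 to 1.43 |
| Constant hazard, median 10 days | 10–70% | 2.18 to 1.41 |
| Constant hazard, median 14 days | 10–70% | 1.81 to 1.38 |
| Constant hazard, median 28 days | 10–70% | 1.37 to 1.25 |
| Failures only in first 14 days, median 5–14 days | 20–50% | 1.31 to 2.09 |
| Failures only in first 7 days, median 5–14 days | 20–50% | 1.15 to 1.52 |
| Failures only in first 3 days, median 5–14 days | 20–50% | 1.07 to 1.21 |
| Only death censored, 47% dead by day 28 (h2 = −ln 0.53/28 = 0.0227) | 10–60% | 1.34 to 1.26 |
| Dead and discharged patients kept as event-free to day 28 | any | 1.0 |

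The 47% is the protocol's ICU mortality figure; placing it at day 28 is an assumption.

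**4. Comparison between arms.** Take two equal latent groups, with daily hazards of organ failure/death/discharge of 0.06/0.06/0.01 (sick) and 0.01/0.005/0.10 (less sick). Let albumin multiply only the death hazards by 0.75. Results to day 28:

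| Quantity | Control | Albumin |
|---|---|---|
| 1-KM, organ failure | 59.6% | 62.2% |
| Cumulative incidence, organ failure | 26.6% | 29.3% |
| ICU death without prior organ failure | 24.6% | 20.4% |
| Organ failure or ICU death (second and third rows before rounding) | 51.2% | 49.6% |

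1-KM and the cumulative incidence of organ failure both rise although treatment does nothing but prevent deaths. Only the death row and the composite show the benefit. With the constant hazards of step 2, cutting the death hazard by 25% (0.03 to 0.0225) leaves 1-KM at 67.4% and raises the cumulative incidence from 32.2% to 34.0%.

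**5. Protocol against SAP.** The protocol's event is a rise from below 2 to at least 2, timed over days 1 to 28. The SAP's organ failure is any subscore above 3, which on the 0–4 scale means a score of 4, reported as a count with no time axis. These are different endpoints, and SAP 6.11 does not mention the difference.

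**The case against.** - **The censoring is inferred.** The protocol states no rule for this endpoint; the rule nearby belongs to length of stay. If dead and discharged patients were kept as event-free to day 28, there would be no overstatement. This stands. Censoring is nevertheless the ordinary reading of a Kaplan-Meier plan, and nothing in either document points to the alternative.
- **The curve may never be produced.** The protocol leaves details of the analyses to the SAP, and SAP 6.7 plans only counts, which carry no Kaplan-Meier inflation. This also stands. But the SAP does not withdraw the curve, and the counts ignore deaths and unequal time in the ICU.
- **A reader might infer a twofold overstatement.** The documents do not support that. A factor near 2 appears only in some of the assumed scenarios; early clustering of failures brings it close to 1, and short ICU stays with a low true risk push it above 3.
- **A reader might infer that cumulative incidence alone cures the comparison between arms.** It does not: in step 4 it rises by about as many points as 1-KM.
- **A reader might infer that prevented deaths would be hidden in the trial report.** They would be missing from this curve only. Mortality at 28, 60 and 90 days, ICU and hospital mortality, and a Kaplan-Meier analysis of mortality are all planned by arm.

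**Conclusion.** The concern holds in a limited form. The protocol names a method that does not estimate the proportion of patients with new organ failure if ICU death and discharge are censored, and it leaves that handling unstated. Given censoring, the overstatement has a definite direction, but its size cannot be fixed from the documents: 1.07-fold to 3.55-fold under the assumed hazards, least when failures come in the first days. It rests on the inferred censoring rule and on assumed event rates and ICU stay. What needs no assumption is that the protocol and the SAP describe different organ-failure analyses under different thresholds and the SAP does not say so. The endpoint is secondary and its comparison exploratory, so neither the primary analysis nor its conclusion is affected. It is still worth correcting, because the change is cheap and a display of organ failure without deaths can mislead about a named objective.

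**What to change.** 1. In SAP 6.7, state that the Kaplan-Meier curve for first organ failure is replaced by the Aalen-Johansen cumulative incidence to day 28, by arm, with death and live ICU discharge as competing events.
2. Always show the cumulative incidence of death by arm beside it.
3. Use the composite of new organ failure or death by day 28 for the comparison between arms. State that death counts wherever it occurs, since vital status is collected at day 28 also after discharge, and that organ failure is observed only in the ICU.
4. Reconcile the definitions: a rise from below 2 to at least 2 in the protocol against any subscore above 3 in the SAP. Use one for both the curve and the counts, or label them as separate endpoints.
5. List these changes in SAP 6.11.

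Cost: some SAP wording and standard programming in the planned SAS. No new data are needed, because daily SOFA, vital status with date of death, and ICU stay are already collected. The downside is one extra curve per arm and one extra composite to report.

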Statistical methods	- Descriptive analysis of all collected data - Primary end-point, 90-day mortality: generalised mixed model with random effects "centre" and "patient in centre" and fixed effects "SAPS II", "SOFA", "baseline serum albumin concentration" and "treatment group" - Secondary outcomes: descriptive analysis - Subgroup analyses according to baseline lactate, baseline quartiles of SOFA, SAPS II and APACHE II - AEs, SAEs and sepsis-related clinical events: frequency	
Financial support	 Deutsche Forschungsgemeinschaft (DFG), Förderkennzeichen: DFG SA 2167/3-1, Projektnummer: 328809707 Instituto GRIFOLS S.A., Barcelona, Spanien Klinik für Anästhesiologie und Intensivtherapie, Universitätsklinikum Jena 	

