- Total amount of fluid administration in the ICU (individual average amount of fluids given enterally or parentrally, including volume therapy) and total fluid balance in the ICU (individual average difference between daily fluid administration urinary output and other fluid loss): descriptive statistics, especially quartiles.

All secondary endpoints, unless included in the primary analysis model, will be exploratively compared using appropriate parametric and nonparametric tests between treatment groups.

Health economics:

In the context of the ARISS study, a health economic cost-benefit analysis of volume replacement therapy of the ICU stay will be carried out up to a maximum of day 28. The direct costs of colloid, crystalloid and albumin administration will be recorded and the length of stay (first hospitalisation and stay since study participation) evaluated economically to assess whether albumin administration has an effect on hospital costs or not. At the patient level, DEALE (declining exponential approximation of life expectancy) (27) will be applied to calculate patient-specific life expectancy based on mortality rates in the general population and in the disease-specific population. The subsequent cost-effectiveness analysis will yield the cost per year of life for albumin administration. The robustness of the analysis will be checked with one-way and multi-way analyses as well as probabilistic sensitivity analysis.

Analysis of safety parameters:

Frequencies of AEs and SAEs will be analysed using frequency tables. In addition, frequencies of selected AEs (sepsis-related clinical events) will be analysed.

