4.3 Secondary Endpoints

- 28- and 60-day-mortality
- Mortality rate at ICU and in-hospital mortality
- SOFA score
- Duration of stay on ICU and duration of hospitalization,
- Days not requiring artificial respiration, days without vasopressors
- Assessment of amount of albumin applicated, other colloids and crystalloids
- · Overall fluid intake, overall fluid balance

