5.1 Missing Values

Single day missing values in GCS (up to 3 consecutive) will be replaced by LOCF for evaluation of daily SOFA score.

All other missing values will be treated as such and not replaced by estimates. Missing values for the primary efficacy parameter 90 day mortality will be respected in Kaplan Meier analysis of mortality.

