6.11 Deviation from Protocol and Amendment

Corresponding to recommendations of reviewers, subgroups with respect to SOFA, SAPS II and APACHE II baseline values are prespecified instead of using quartiles.

7 Software and Validation

Analysis will be performed with SAS Version 9.4 or higher.

Validation plan:

All programs will be validated on either a basic or an enhanced validation level. Basic validation level means validation by the programmer according ZKS Jena SOP Bi06 and includes check of program code, check of log-file and check of output. Enhanced validation will be performed by an independent programmer and includes enhanced check of program code, log-file and output. Primary efficacy analysis will be validated by independent duplicate programming. Results of adverse events analysis will be cross-checked with the contents of the safety data base.

Programms for DSUR and SMC reports will be validated on basic validation level by the respective programmer.

Analysis	Validation level
Population characteristics and baseline data	basic
Previous and concomitant diseases and therapies	basic
Exposition to therapy / compliance	basic
Primary analysis	enhanced
Secondary analyses	basic
Adverse events	basic
Laboratory parameters	basic
Other safety data	basic

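### Ventilator- and vasopressor-free days stop at first ICU discharge with no rule for deaths, so an early live discharge can score below a long ICU stay or an ICU death

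*Protocol*

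**What the plan says.** Protocol 11.3.2, under secondary endpoints, gives the only counting window for these endpoints: "Ventilation-free days, vasopressor-free days until (first) discharge of ICU or maximum 28 days: descriptive statistics". Protocol 3.2 names them without a window.

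The SAP adds no rule. Section 4.3 lists "Days not requiring artificial respiration, days without vasopressors". Section 6.7 assigns "Duration of stay on ICU and duration of hospitalization, days not requiring artificial respiration" and days without vasopressors to descriptive analysis. Section 6.11, on deviations from the protocol, says only that "subgroups with respect to SOFA, SAPS II and APACHE II baseline values are prespecified instead of using quartiles". The protocol's window therefore stands.

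No section says how a patient who dies is scored. The nearest statement concerns length of stay, which 11.3.2 analyses by "descriptive statistics, Kaplan-Meier estimates, censored after drop-out and death". SAP 5.1 says "All other missing values will be treated as such and not replaced by estimates", but that is a missing-data rule and settles neither death nor time after discharge.

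On the use of these endpoints, the synopsis (Protocol 1.1) says "Secondary outcomes: descriptive analysis", while 11.3.2 says secondary endpoints will be "exploratively compared using appropriate parametric and nonparametric tests between treatment groups".

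On the data, Protocol 7.5 runs daily visits only while the patient is in the ICU. Section 7.5.1 makes a return to the ICU irrelevant for endpoints and records the first ICU stay. Section 7.5.2 records vital status and date of death at days 28, 60 and 90.

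**The concern.** A free-day count should reward coming off support early and surviving. When counting ends at ICU discharge, it measures how long a patient stayed in the ICU after support ended. Prompt recovery and discharge then lower the score, and a lingering ICU stay raises it. With no death rule, a patient who comes off support and later dies in the ICU can keep the days accrued before death and outscore an early survivor.

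ICU length of stay is itself a secondary endpoint, so an effect on it is one the trial sets out to look for. If albumin shortens both support and the ICU stay that follows, these counts could show nothing or point the wrong way. The answer would also depend on a death rule chosen at programming. In an open-label trial that rule should be fixed before arm-level results are seen.

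**Working it through.** The plan gives no expected value for these endpoints, so there is no figure to reproduce. The check scores example patients first and then whole arms.

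**1. Individual patients.** As written: min(28, day of ICU exit) − day support ended, taking ICU death as an exit because no other rule is given. Comparison rule (an assumption, not in the documents): 28 − day support ended, or 0 if dead by day 28.

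| Patient | As written | Fixed 28 days |
|---|---|---|
| Off support day 2, discharged alive day 4 | 4 − 2 = 2 | 28 − 2 = 26 |
| Off support day 10, discharged alive day 20 | 20 − 10 = 10 | 28 − 10 = 18 |
| Off support day 2, discharged alive day 5 | 5 − 2 = 3 | 26 |
| Off support day 3, ICU death day 14 | 14 − 3 = 11 | 0 |

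The order reverses both between the first two patients and between the last two.

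**2. Whole arms.** Inputs:
- From the documents: ICU mortality 47% (Protocol 8.2, a figure for severe sepsis and septic shock together) and 706 patients per arm (Protocol 11, sample size).
- Assumed: one support episode, exponential with mean 7 days; then an ICU stay off support, exponential with mean 7 days; a constant daily death risk d throughout the ICU stay; no death after live ICU discharge.

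With λ = 1/7, live ICU exit has probability [λ/(λ+d)]². Setting this to 0.53 gives d = 0.0534.

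Write r = λ + d. The means are
- as written: W = λ[1 − e^(−28r)(1 + 28r)]/r²
- fixed: F = (λ²/r)[28/r − (1 − e^(−28r))/r²] + (λd/r)e^(−28r) × 28²/2

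Control: λ = 0.1429, r = 0.1962, so W = 3.6 and F = 12.2.

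Both periods 15% shorter: λ = 1/5.95 = 0.1681, r = 0.2214, so W = 3.4 and F = 13.6. ICU mortality becomes 1 − (0.1681/0.2214)², about 42%.

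Both periods 30% shorter: W = 3.1, F = 15.2, ICU mortality 37%.

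Only support 30% shorter: W rises to 4.0 and F to 14.0.

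**3. Simulated trials, two-sided 0.05.**

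| Both periods shorter by | As written, t-test | As written, rank test | Fixed 28 days |
|---|---|---|---|
| 15% | harm in about 15–17% | close to its nominal error rate | benefit in 57–59% |
| 30% | harm in 69%, benefit in none | harm 4%, benefit 1% | benefit in over 99% |

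The unwritten death rule matters by itself. In the 30% case, if counting still stops at discharge but deaths score 0, the mean goes from 2.7 to 2.4, the t-test shows harm in 22%, and the rank test shows benefit in 43%.

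**4. Other assumptions.** With mean periods of 5+5, 8+4 or 4+8 days, or ICU mortality of 35%, and both periods 30% shorter, the mean as written falls by 15–21% and the fixed count rises by 16–24%. With support 30% shorter, the count as written falls once the later ICU stay shortens by more than 6.5–13%, depending on the setting.

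**5. Length of stay (separate).** Assume a constant exit rate with 53% of exits alive. At day 28, one minus Kaplan-Meier with deaths censored is 1 − exp(−0.53 × 28/mean stay). The true proportion discharged alive is 0.53 × [1 − exp(−28/mean stay)]. For a mean stay of 14 days these are 65% and 46%; for 10 days, 77% and 50%.

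**The case against.** The window matches the data. Support is recorded only in the ICU and readmission is not used, so crediting later days means assuming what was not observed. A simple credit would also give free days to a patient who leaves the ICU still ventilated, for example on transfer. This stands, and it shapes the fix. It does not rescue the stated rule, which in effect gives no credit for time alive after discharge.

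A reader might infer from the 69% figure that the trial would probably report significant harm. The documents do not support that. The figure needs both periods 30% shorter, which in this model means about 10 points fewer ICU deaths, against the 7.5-point fall in 90-day mortality the trial is designed to detect. It also needs a t-test, although 11.3.2 allows nonparametric tests and requires medians and quartiles. In the same scenario the rank test shows harm in 4%. The documents give no distributions of support or stay, so every arm-level size here is conditional on assumptions.

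A reader might also infer that any faster weaning lowers the count. It does not: if only support shortens, both counts rise.

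Finally, the consequence is limited. The synopsis and SAP treat these endpoints as descriptive, the between-arm tests in 11.3.2 are exploratory, and mortality is reported alongside. That lowers the weight but leaves the rule wrong.

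**Conclusion.** The point holds as a defect in how two secondary endpoints are scored, and it should be fixed. The individual inversion follows by arithmetic from the wording of 11.3.2, with ICU death taken to end the count. At arm level the main loss is masked benefit: with both periods 15% shorter, a fixed count detects benefit in 57–59% of simulated trials, while the count as written drifts slightly downward. Significant apparent harm is a lesser risk that depends on the test. All arm-level sizes rest on the assumed exponential model and a cited 47% ICU mortality, and the inversion requires the ICU stay after support to shorten as well.

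The primary endpoint and the sample size are unaffected.

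The Kaplan-Meier rule for length of stay is a separate, minor matter. It misleads only if one minus the curve is read as the probability of live discharge. The plan does not say it will be read that way, and SAP 6.7 neither repeats nor replaces the rule.

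**What to change.** In Protocol 11.3.2 and SAP 6.7:

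- Define free days over fixed days 1–28 as days alive without the support in question.
- State a score for death by day 28, for example 0, and compare arms with a rank-based test.
- Credit days after live ICU discharge as free only if the support had ended by discharge.
- State a separate rule for patients discharged or transferred on support, for example no credited days, with a sensitivity analysis.
- State that support after discharge and on readmission is unrecorded and assumed absent.
- Report deaths, and support days in survivors, alongside the composite.

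Separately, present time to live ICU or hospital discharge as cumulative incidence with death as a competing event (Aalen-Johansen), with the same rule in SAP 6.7.

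The cost is wording and standard code. Daily ICU support, ICU discharge and date of death are already collected. There are two drawbacks: post-discharge days are credited on an assumption, and a death score of 0 makes the endpoint partly a mortality measure, which is why its components should be shown.
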